2 INTRODUCTION AND RATIONALE

Cataract surgery is the most commonly performed procedure by the ophthalmic surgeon. It is estimated that more than 26 million cataract operations with intraocular lens (IOL) implantation were to be performed worldwide in 2017.¹ The average age of cataract patients is reported to be 65 to 70 years old, with a small percentage of cataract surgeries being performed on patients as young as in their early 40's.^{2,3} While key cataract technology advancements have resulted in important reductions in residual refractive error and improved uncorrected visual acuity, significant postoperative residual refractive error remains the most frequent cataract surgery complication. RxSight's Light Adjustable Lens (LAL) addresses the problems of residual refractive error by allowing adjustment of the spherical and cylindrical power postoperatively. The Center for Devices and Radiological Health (CDRH) of the Food and Drug Administration (FDA) approved RxSight's premarket approval (PMA) application for the LAL and Light Delivery Device (LDD) system on November 22, 2017. The system is indicated for the reduction of residual astigmatism to improve uncorrected visual acuity after removal of the cataractous natural lens by phacoemulsification and implantation of the intraocular lens in the capsular bag; in adult patients:

- With pre-existing corneal astigmatism of ≥ 0.75 diopters
- Without pre-existing macular disease

The system also reduces the likelihood of clinically significant residual spherical refractive errors.

Presbyopia, which will affect approximately 2.1 billion people by 2020, is the irreversible loss of the accommodative ability of the eye that occurs due to aging.⁴ Accommodation refers to the ability of the eye to increase the refractive power of its crystalline lens in order to focus near objects on the retina.⁵ Presbyopia typically occurs in people over 40 years of age and can cause a considerable decrease in the quality of life for many of those affected.⁶ Without correction, presbyopia results in difficulty performing tasks at a customary working distance. Because most patients have daily activities that require them to read and work at near and with the increasing importance of intermediate vision to clearly see cell phones and computer monitors, patients are seeking treatment options to mitigate the effects of their presbyopia.

The vast majority of cataract surgery patients are presbyopic preoperatively and all patients will experience presbyopia after cataract surgery. Cataract surgery presents patients with an

¹ Eyewiretoday. Steady Growth in Cataract Surgical Procedures is Expected Over the Next 5 Years, July 27, 2017.

² Cummings A. The Influence of Age on Refractive Cataract Surgery. CRSTEurope. Feb 2011.

³ Gollogly H, Hodge D, St. Sauver J, Erie J. Increasing incidence of cataract surgery: Population –based study. J Cataract Refract Surg 2013; 39:1383-1389.

⁴ Arlt EM, Krall EM, Moussa S, Grabner G, Dexl A. Implantable inlay devices for presbyopia: the evidence to date. Clin Ophthalmol. 2015 Jan 14;9:129-137.

⁵ American Optometric Association. Care of the patient with presbyopia. St. Louis (MO): American Optometric Association; 2010.

⁶ McDonnell PJ, Lee P, Spritzer K, Lindblad AS, Hays RD. Association of presbyopia with vision-targeted health-related quality of life. Arch Ophthalmol. 2003;121(11):1577-1581.

opportunity to not only remove the cataractous lens, but also to have presbyopia mitigated through the implantation of specific IOLs. Current techniques include the use of pseudophakic monovision and multifocal IOLs.

Pseudophakic monovision is a concept in which 1 eye (usually dominant) is targeted for distance vision and the other eye is targeted for near vision after IOL implantation. Depending on the technique, target refraction of the non-dominant eye ranges from 1.00 to 2.50 diopters (D) of myopia.⁷ Obtaining a pre-determined magnitude of anisometropia (i.e. refractive accuracy of the IOL implantation) between eyes is critical to achieving patient satisfaction as any inaccuracy could lead to inadequate distance or near vision or patient non-adaptation to the amount of anisometropia.

Multifocal IOLs can be refractive, diffractive, or hybrid diffractive-refractive. Diffractive multifocal IOLs use light diffraction to produce 2 focal points, one for distance vision and one for near vision. In refractive multifocal IOLs, refractive power changes from the center to the periphery of the IOL, thus producing many focal points. Recent studies of multifocal IOLs report good results for both near and distance vision in terms of spectacle independence, but these IOLs are frequently associated with a number of visual adverse effects, such as dysphotopsia, visual disturbances at night, halos, and glare.⁷

This study aims to explore the treatment of the LAL postoperatively either with light treatment patterns intended to mitigate the effects of postoperative residual error only and/or combined with light treatment patterns that are intended to mitigate the effects of presbyopia by enhancing the patient's intermediate and near vision. This latter mitigation is accomplished by designing the light treatment pattern to create a distribution of optical powers within the LAL. Light treatment patterns mitigating the effects of postoperative residual error will be evaluated by looking at postoperative uncorrected distance visual acuity while light treatment patterns intended to mitigate the effects of presbyopia will be evaluated by looking at postoperative uncorrected distance, intermediate and near visual acuity.

⁷ Labiris G, Giarmoukakis A, Patsiamanidi M, et al. Mini-monovision versus multifocal intraocular lens implantation. J Cataract Refract Surg 2015; 41:53-57.

3 STUDY OBJECTIVE

The objective of this study is to evaluate, for the visual correction of aphakia, whether the RxSight Light Adjustable Lens (LAL) and Light Delivery Device (LDD) can be used to improve visual outcomes after performing adjustments of the LAL with the LDD. This is an exploratory study. No primary effectiveness endpoints will be defined.

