7.4 EXAMINATION SCHEDULE

Evaluation	Subjects who did not previously participate in CSP-037-MX or Former CSP-037-MX subjects with fellow eye (CSP-037-MX non-study eye) enrolled	Former CSP-037-MX subjects with only former CSP-037-MX study eye enrolled
Preoperative	Day -60 to Day -1	NA
Operative	Day 0, day of surgery	NA
Postop Day 1	Days 1 to 2 postop	NA
¹	Days 7-14 postop	NA
Postop Week 3	Days 17 to 30 days postop: Adjustment #1	Days 17 to 30 days postop: Adjustment #1
Adjustment #2, if needed	2 to 7 days post Adjustment #1	2 to 7 days post Adjustment #1
Adjustment #3, if needed	2 to 7 days post Adjustment #2	2 to 7 days post Adjustment #2
Lock-in #1	2 to 7 days post final adjustment	2 to 7 days post final adjustment
Lock-in #2, if needed	2 to 7 days post lock-in #1	2 to 7 days post lock-in #1
Post Lock-in	7 to 14 days post final lock-in	7 to 14 days post final lock-in
Postop Month 3	Days 90 to 150 postop	Days 90 to 150 postop
Postop Month 6 or later	Days 180 to 400 postop	Days 180 to 400 postop

¹ Subgroup of eyes determined by the principal investigator

Unscheduled visits falling outside the designated ranges for scheduled visits will be considered “interim” visits for data recording purposes. A report form will be completed for interim visits on the study eye.

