³ Tests indicated with an “X” must be performed at each unscheduled visit. Other tests may be conducted based on the investigator’s assessment of the subject.

⁴ Only required for subjects who previously participated in RxSight’s CSP-037-MX study

*Visits only required for subjects who did not previously participate in RxSight’s CSP-037-MX study

**Subgroup of eyes based on decision made by Principal Investigator

Visits	Preop*	Preop*	Operative*	Postop Day 1*	Postop Day 1*	Postop Week 3	Postop Week 3	Adjustment #2 (if needed)	Adjustment #3 (if needed)	Lock-in #1	Lock-in #2 (if needed)	Postop Month 3	Postop Month 3	Postop Month 6 or later	Unscheduled Visit ³
Visits	Preop*	Operative*	Operative*	Postop Day 1*	Postop Day 1*	Postop Week 3	Postop Week 3	Adjustment #2 (if needed)	Adjustment #3 (if needed)	Lock-in #1	Lock-in #2 (if needed)	Post Lock-in	Post Lock-in	Postop Month 6 or later	Unscheduled Visit ³
Anterior Segment OCT				X	X	X	X	X	X	X	X	X	X	X	
Posterior Segment SD-OCT					X ²	X ^{2, 5}					X ²				
Vision Quality Measurement				X	X	X	X	X	X	X	X	X	X	X	
Monocular Uncorrected Distance Visual Acuity (UCDVA)	X			X	X	X	X	X	X	X	X	X	X	X	X
Binocular Uncorrected Distance Visual Acuity					X ¹	X ^{1, 1, 2}					X ^{1, 2}	X ^{1, 2}	X ^{1, 2}		
Manifest Refraction	X				X	X	X	X	X	X	X	X	X	X	
Monocular Best Corrected Distance Visual Acuity (BCDVA)	X				X	X	X	X	X	X	X	X	X	X	
Ocular Dominance Test	X				X	X ⁵									
DOF Testing					X ²	X ^{2, 5}			X ²		X ²	X ²	X ²		
Monocular Distance Corrected Intermediate Visual Acuity					X ²	X ^{2, 5}			X ²		X ²	X ²	X ²		
Monocular Distance Corrected Near Visual Acuity					X ²	X ^{2, 5}			X ²		X ²	X ²	X ²		

¹ Only performed on subjects with both eyes enrolled and successfully implanted

^{1,1} Only performed on subjects with both eyes enrolled and successfully implanted and subject did not have an visit.

² May be performed on a subgroup of subjects as described in section 7.3.2.2 of the protocol

³ Tests indicated with an "X" must be performed at each unscheduled visit. Other tests may be conducted based on the investigator's assessment of the subject.

⁴ Only required for subjects who previously participated in RxSight's CSP-037-MX study.

⁵ Only performed on subjects who did not have an [REDACTED] visit.

*Visits only required for subjects who did not previously participate in RxSight's CSP-037-MX study.

** Subgroup of eyes based on decision made by Principal Investigator.

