8.1.1 EXPLORATORY EFFECTIVENESS PARAMETERS

Primary Exploratory Parameters

Eyes that received only non-presbyopic adjustments.

- % of eyes with UCDVA of 20/20 or better at Postop Month 6 or later

Eyes that received a presbyopia adjustment.

- Proportion of eyes simultaneously with (1) Monocular UCDVA of 20/25 or better and (2) Monocular UCIVA of 20/32 or better and (3) Monocular UCNVA of 20/40 or better at Postop Month 6 or later.

Clinical data for former CSP-037-MX study eyes may be analyzed separately.

Additional Exploratory Parameters

UCDVA

Monocular and/or binocular UCDVA will be presented with the number and percent of eyes that fall into each category of visual acuity performance (e.g. 20/20 or better, 20/25 or better, 20/32 or better, etc.) at each visit tested. Number and percent for eyes that only received non-presbyopic adjustments and for eyes that received a presbyopia adjustment may be presented separately. In addition, clinical data for former CSP-037-MX study eyes may be analyzed separately.

UCIVA, UCNVA, DCIVA, and DCNVA

Monocular and/or binocular UCIVA, UCNVA, DCIVA, and DCNVA for eyes that received a presbyopia adjustment will be presented with the number and percent of eyes that fall into each category of visual acuity performance (e.g. 20/20 or better, 20/25 or better, 20/32 or better, etc.) at each visit tested. In addition, clinical data for former CSP-037-MX study eyes may be analyzed separately.

Depth of Focus

The mean acuity across all eyes that received a presbyopia adjustment will be calculated and plotted separately. The mean, standard deviation, and confidence intervals for each point on the curve will be reported. In addition, clinical data for former CSP-037-MX study eyes may be analyzed separately.

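### The objective is improvement after adjustment, but the visible analysis text specifies no within-eye change in uncorrected acuity from before adjustment

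*Combined protocol and SAP*

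**What the plan says.** Section 3 gives the objective as whether the lens and the light delivery device "can be used to improve visual outcomes after performing adjustments of the LAL with the LDD". It adds: "This is an exploratory study. No primary effectiveness endpoints will be defined". Under Section 4 all eyes are treated, and there is no untreated comparison group.

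Section 8.1.1 nevertheless names primary exploratory parameters, one per adjustment group:

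- Non-presbyopic adjustments only: the percentage "of eyes with UCDVA of 20/20 or better at Postop Month 6 or later".
- Presbyopia adjustment: "Proportion of eyes simultaneously with (1) Monocular UCDVA of 20/25 or better and (2) Monocular UCIVA of 20/32 or better", together with a near criterion of 20/40, again at Month 6 or later.

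Neither has a baseline term. The additional exploratory analyses in the same section are category counts at each visit: "Monocular and/or binocular UCDVA will be presented with the number and percent of eyes that fall into each category of visual acuity performance", and "Monocular and/or binocular UCIVA, UCNVA, DCIVA, and DCNVA for eyes that received a presbyopia adjustment will be presented" in the same form. Splitting the UCDVA table by adjustment group is optional.

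Section 8.2.2 plans a within-eye change for BCDVA only, in seven letter-gain and letter-loss categories, measured from Week 3 or from the preoperative visit.

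In Section 7.4 the Week 3 visit is the visit of the first adjustment ("Days 17 to 30 days postop: Adjustment #1"). In Table 1 the monocular UCDVA row is marked at Week 3 and at Month 6 without a subgroup footnote. Section 7.3.2.2 lists monocular UCIVA, UCNVA, DCIVA and DCNVA among optional tests for subgroups that the Principal Investigator may choose.

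**The concern.** An eye that already sees 20/20 uncorrected after cataract surgery, before any light treatment, counts as a success exactly like an eye brought there by the adjustment. An eye that had 20/20 at Week 3 and lost it counts as a failure exactly like one that never had it. Eligibility adds to this: newly implanted eyes must be projected to reach 20/20 best-corrected after surgery (Section 6.1), so a good Month 6 rate partly reflects selection and cataract removal.

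The direction of change matters for safety as well as benefit. Section 10.6 warns that light treatment may fail to improve vision or may worsen it. No specified analysis counts the eyes whose uncorrected acuity fell after treatment.

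**Working it through.** The plan states no power, sample-size or expected-rate figure for these parameters, so there is nothing of its own to reproduce. The check is what two per-visit percentages can and cannot reveal about the same eyes.

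**Inputs.** The thresholds and visits come from Sections 7.4 and 8.1.1. The documents give no acuity rates, so those below are assumptions.

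**Formula.** Of n eyes, let A be at the threshold at Week 3 and B at Month 6.

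- Eyes that lost the threshold lie between max(0, A − B) and min(A, n − B).
- Eyes that gained it = eyes that lost it + (B − A).

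**Main example, n = 100, A = 40, B = 80.**

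- Lost: from max(0, 40 − 80) = 0 to min(40, 100 − 80) = 20.
- Gained: from 0 + 40 = 40 to 20 + 40 = 60.
- Net: 80 − 40 = 40 eyes, whichever case holds.

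**Other assumed rates, n = 100.**

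| Week 3 | Month 6 | Net | Gained | Lost |
|---|---|---|---|---|
| 20 | 70 | 50 | 50 to 70 | 0 to 20 |
| 40 | 70 | 30 | 30 to 60 | 0 to 30 |
| 50 | 80 | 30 | 30 to 50 | 0 to 20 |
| 60 | 60 | 0 | 0 to 40 | 0 to 40 |

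The per-visit tables fix the net column and leave the last two open. A paired table replaces each range with a count.

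**How much of the headline rate predates adjustment.** For the same Month 6 rate of 80%, a Week 3 rate of 20% leaves a net 80 − 20 = 60 points, and a Week 3 rate of 60% leaves 80 − 60 = 20 points. The primary parameter reads 80% in both cases.

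**Whether other planned tables close the gap.**

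- UCDVA by visit: the wording allows monocular or binocular results and makes the group split optional, so even the net monocular change within each group is not assured.
- Presbyopia composite: it requires three criteria in the same eye at once and is specified only at Month 6. Separate tables for each distance cannot rebuild it at Week 3.
- BCDVA change: it is within-eye, but best correction largely removes the residual refractive error that a spherocylindrical adjustment targets, and the choice of baseline is open.

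**The case against.** The strongest reply is that the study is openly exploratory, with no hypothesis, and that Section 2 says treatment will be evaluated by looking at postoperative uncorrected acuity. Levels were a declared choice. That excuses the absence of a test and of a sample-size argument. It does not make a Month 6 level an answer to a question about improvement.

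A reader might go further and infer that the trial cannot say how many eyes improved or worsened. The documents do not support that. Monocular UCDVA is scheduled for all eyes at Week 3 and Month 6, so the paired result can be produced. The per-visit tables allow some net comparison, and Sections 4 and 5 leave room for further analyses, though they name none.

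A reader might also infer that harm would go unseen because BCDVA is insensitive to adjustment. That is too strong as well. Sections 2, 7.1.1 and 7.1.5 describe presbyopia patterns that spread optical power, create multifocality and introduce spherical aberration, which could plausibly lower best-corrected acuity. Section 10.6 names possible ultraviolet damage to cornea and retina. The planned BCDVA loss categories are relevant to both. They would miss an eye whose refraction moved the wrong way but can still be corrected with a lens.

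Three limits stand. The upper bound in the main example is extreme: half of the 40 eyes already at 20/20 must lose it while all 60 others gain it. Crossing 20/20 can be a change of one letter, so losing the threshold is not the same as being made worse. And Section 8 is visibly incomplete (numbering passes from 8.2 to 8.2.2, and footnote 8 has no anchor), so the point applies to the visible text.

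**Conclusion.** The point holds as a gap between the objective and the specified analysis; it is not a numerical error. In the visible text, no within-eye change in uncorrected acuity from before adjustment is specified, and the headline rates combine the result of cataract surgery and lens power choice with that of adjustment. At assumed rates of 40% and 80%, the planned tables are compatible with anything from 0 to 20 eyes per 100 losing 20/20. The range depends entirely on those assumed rates.

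For UCDVA the gap closes with data already scheduled. For the presbyopia composite it is harder, because pre-adjustment UCIVA and UCNVA are optional subgroup tests. A paired change would still be uncontrolled, since healing between Week 3 and Month 6 also contributes. The change is worth making because it costs almost nothing and bears directly on the stated objective.

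**What to change.** In Sections 5 and 8.1.1, add for each adjustment group:

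1. **Baseline.** The last monocular UCDVA before the eye's first light treatment. This is normally the Week 3 value taken before the first adjustment. The rule should be tied to the first light treatment because what some eyes receive at days 7 to 14 is redacted, and footnote 5 of Table 1 drops some Week 3 tests for eyes that had that visit.
2. **Paired UCDVA, baseline to Month 6 or later.** A 2×2 table (kept, gained, lost, never) at the group's own threshold: 20/20 for non-presbyopic eyes and 20/25 for presbyopia eyes. Add the change in logMAR UCDVA, with the letter-gain and letter-loss categories already used for BCDVA, so that one-letter crossings are not over-read.
3. **Presbyopia eyes.** The paired composite and the changes in UCIVA, UCNVA, DCIVA and DCNVA, only in eyes with pre-adjustment measurements. State how many there are, and that the investigator selected this subset.
4. **BCDVA change from the same baseline, shown alongside.** Do not rely on the difference between UCDVA and BCDVA: a treatment-caused loss that lowers both equally would leave it unchanged.
5. **Wording.** Describe the paired change as uncontrolled.

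The cost is a few lines of text and some extra tables. UCDVA and BCDVA need no new visits or tests. The sponsor's downside is that the benefit may look smaller than the Month 6 rate. A composite change for all presbyopia eyes, instead of a subset, would require making the optional pre-adjustment tests mandatory.

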4 STUDY DESIGN

A prospective, single center, exploratory study will be conducted. Subjects will be followed until completion of the Postop Month 6 or later follow-up visit.

Patients who require cataract extraction and intraocular lens implantation will be pre-screened for eligibility as part of pre-entry activity. If one or both eyes meet inclusion/exclusion criteria, delegated and trained study staff will explain the study purpose, procedures, risks/benefits and subject responsibilities to the potential participant. Written informed consent must be obtained prior to initiation of any clinical procedures that are performed solely for the purpose of determining eligibility for research. The patient is enrolled upon signing the informed consent. Both eyes of all subjects may be screened for eligibility at the same preoperative visit. If at any time during the preoperative visit, an eye does not meet inclusion or exclusion criteria, screening for that eye can be discontinued immediately. If only one eye is being screened, then the subject will be exited from the study. If both eyes of the subject are enrolled for study participation, each eye will be scheduled for surgery within a timeframe of the investigator's choice but on separate days.

Patients from RxSight's CSP-037-MX study may have both eyes screened for study eligibility. The former CSP-037-MX study eye must meet all inclusion/exclusion criteria as specified below for subjects who previously participated in CSP-037-MX. If applicable, the fellow eye (CSP-037-MX non-study eye) must meet all inclusion/exclusion criteria as specified below for subjects who did not previously participate in CSP-037-MX. If only the prior CSP-037-MX study eye is being considered for this study, the subject will need to review and sign only a CSP-036-MX written informed consent for former CSP-037-MX subjects. If both eyes are being considered for this study, the subject will also have to review and sign a CSP-036-MX written informed consent for subjects who had no affiliation with CSP-037-MX.

At the discretion of the Principal Investigator, a subgroup of eyes will receive an [REDACTED] 7-14 days postop. Commencing 17 to 30 days postop, all eyes will receive up to three adjustments and one to two lock-in treatments. Each light treatment will be separated by 2 to 7 days. The type of adjustment (spherocylindrical and/or presbyopia) the study eye receives is dependent on specific criteria at each light adjustment visit. Postoperatively, all subjects will undergo ophthalmic examinations until completion of the Postop Month 6 or later follow-up visit.

For subjects that receive only non-presbyopic adjustments, uncorrected distance visual acuities will be presented and summarized. For subjects that receive a presbyopia adjustment, uncorrected distance, uncorrected intermediate and uncorrected near acuities will be presented and summarized. Additional analyses may be performed. Safety for all study eyes will be evaluated per ISO 11979-7.

5 OUTCOME PARAMETERS

The following visual performance parameters will be collected and summarized for eyes that received only non-presbyopic adjustments.

- % of eyes with UCDVA of 20/20 or better at Postop Month 6 or later.

The following visual performance parameters will be collected and summarized for eyes that received a presbyopia adjustment.

- Proportion of eyes simultaneously with (1) Monocular UCDVA of 20/25 or better and (2) Monocular UCIVA of 20/32 or better and (3) Monocular UCNVA of 20/40 or better at Postop Month 6 or later.

Additional analyses may be performed. Clinical data for eyes receiving only non-presbyopic adjustments and eyes receiving a presbyopia adjustment may be summarized and analyzed separately. In addition, clinical data for former CSP-037-MX study eyes may be analyzed separately.

Safety Parameters:

- Incidence of persistent sight-threatening complications and adverse events and cumulative events defined per ISO 11979-7.

The incidence of all other adverse events will also be presented.

